 - h. The MOAA/S will be performed every 15 minutes from predose to $t=+1.5$ hours postdose. Pulse oximetry will be performed every 15 minutes from predose to $t=1.5$ hours postdose.
 - i. The BPRS+ and CADSS to be performed predose and at 40 minutes and 1.5 hours postdose.
 - j. CGADR to be performed at 1 hour and 1.5 hour postdose; if the response is not “Yes” at 1.5 hour postdose, the assessment will be repeated every 15 minutes until a “Yes” response is achieved or until the subject is referred for appropriate medical care if clinically indicated. A subject should not be discharged prior to the 1.5 hour time point.
 - k. PK blood collection will be performed at $t=40$ minutes, $t=1$ hour and $t=2$ hours postdose (where $t=0$ is defined as the time of the first intranasal spray on PK blood collection Day).
 - l. Blood samples should be collected prior to dosing. It is preferred that subjects adhere to a low fat diet on the day of sample collection. Subjects also should refrain from strenuous exercise for 24 hours prior to sample collection.
 - m. Visit 3.10 will be identical to the start day of the posttreatment phase.
 - n. Pulse oximetry only.
 - o. Informed consent must be obtained prior to the initiation of any study procedure including washout of prohibited therapies.
 - p. MADRS interview should not be conducted on the same day with the assessment at Visit 3.9.

TIME AND EVENTS SCHEDULE 2 [-POSTTREATMENT PHASE AND FOLLOW-UP PHASE]

Visit number	Posttreatment Phase											Follow-up Phase ^a	
	4.1	4.2	4.3	4.4	4.5	4.6	4.7	4.8	4.9, 4.10, 4.11, 4.13, 4.14, 4.15, 4.17, 4.18, 4.19, 4.21, 4.22, 4.23	4.12 4.16 4.20 4.24	EW	6.1 6.2	6.3
Study week	5	6	7	8	9	10	11	12	13, 14, 15, 17, 18, 19, 21, 22, 23, 25, 26, 27	16 20 24 28	-	F1 F2	F4
Study day	32	39	46	53	60	67	74	81	88, 95, 102, 116, 123, 130, 144, 151, 158, 172, 179, 186	109 137 165 193	-	F7 F14	F28
Clinic visit or remote MADRS window (days)	+3	±3	±3	±3	±3	±3	±3	±3	±3	±3	-	±3	±3
Clinic (C) or remote MADRS interview only (RM)	C	C	C	C	RM	C	RM	C	RM	C	C	C	C
Safety Assessments (Clinician-completed)													
C-SSRS: Since last visit version	X	X	X	X		X		X		X	X	X	X
PWC-20	X	X	X	X								X	X
Safety Assessments (Subject-completed)													
POMS-2	X	X		X		X		X		X	X	X	X
Efficacy Assessments (Clinician-completed)													
MADRS (7-day recall)	Performed weekly^{b, c}											X	X
CGI-S	X	X	X	X		X		X		X	X	X	X
Efficacy Assessments (Subject-completed)													
SDS		X		X		X		X		X	X		

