- Hospitalization for worsening depression or any other clinically relevant event determined per clinical judgment to be suggestive of a relapse of depressive illness such as suicide attempt, completed suicide, or hospitalization for suicide prevention. If hospitalized for any of these events, the start date of hospitalization will be used for the date of relapse. Otherwise the date of the event will be used if the subject is not hospitalized.

In case both relapse criteria are met, the earlier date will be defined as the date of relapse for this subject.

Subjects who relapse within 20 weeks after the start of the posttreatment phase will transit to an OL induction phase and receive 4 weeks of OL treatment with intranasal esketamine (28, 56, or 84 mg). Subjects who relapse more than 20 weeks after the start of the posttreatment phase will withdraw from the study and clinical/standard-of-care treatment will be arranged by the study investigator after relapse. Subjects who do not experience relapse throughout this 24-week posttreatment phase will complete study without the 4-week follow-up phase (see Section 9.2.1.2.3).

Subjects who meet the criteria of relapse, they need to join OL induction phase before next remote MADRS assessment.

In the first 4 weeks of the posttreatment phase, withdrawal or rebound symptoms or both and potential abuse-liability will be evaluated using Physician's Withdrawal Checklist, 20-item (PWC-20) and Profile of Mood States, 2nd Edition (POMS-2).

The oral antidepressant medication initiated from the prospective lead-in phase, which will continue to be ongoing and stable during the double-blind induction phase will also be maintained throughout this phase.

Open-label Induction Phase

Subjects who relapsed in the posttreatment phase will receive a 4-week OL induction treatment course of intranasal esketamine. The beginning of the OL induction phase should be at least 2 weeks (14 calendar days) after the last dose in the double-blind induction phase. Subjects who meet the relapse criteria before 2 weeks after the last dose in the double-blind induction phase will not have an option for joining open label induction phase. They will withdraw from the posttreatment phase and move forward to the follow up phase.

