The ECG variables that will be analyzed are heart rate, PR interval, QRS interval, QT interval, and corrected QT (QTc) interval using the following correction methods: QT corrected according to Bazett's formula (QTcB) and QTcF.^{2,31,60}

Descriptive statistics of QTc intervals and changes from baseline will be summarized at each scheduled time point. The percentage of subjects with QTc interval >450 milliseconds, >480 milliseconds, or >500 milliseconds will be summarized, as will the percentage of subjects with QTc interval increases from baseline >30 milliseconds or >60 milliseconds.

All clinically relevant abnormalities in ECG waveform that are changes from the baseline readings will be reported (eg, changes in T-wave morphology or the occurrence of U-waves).

Vital Signs

Descriptive statistics of temperature, heart rate, pulse oximetry, respiratory rate, and blood pressure (systolic and diastolic) (supine) values and changes from baseline will be summarized at each scheduled time point. The percentage of subjects with values beyond clinically important limits will be summarized.

Physical Examination

Results of physical examinations (abnormalities) will be listed.

C-SSRS

Suicide-related thoughts and behaviors based on the C-SSRS will be summarized by treatment group in incidence and shift tables. Separate endpoints for suicidal ideation and suicidal behavior will be defined and summarized descriptively by treatment group. Missing scores will not be imputed.

PWC-20, CADSS, CGADR, MOAA/S, BPRS+, and POMS-2

Physician Withdrawal Checklist; 20-item (PWC-20) rating scale, dissociative data from the CADSS, alertness data from the CGADR, sedation data from the MOAA/S, psychosislike effect data from the BPRS+ and abuse-liability data from POMS-2 will be summarized descriptively at each scheduled visit by treatment group.

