| Parameter | Analysis Phase | Scheduled Day ^a | Time Interval (label on output) | Time Interval ^a (Day) | Target Time Point ^a (Day) | |
|-----------|--------------------|----------------------------|---------------------------------|----------------------------------|--------------------------------------|----|
| | | OL 8 | Day 8 (OL) | 2-11 | 8 | |
| | | OL 15 | Day 15 (OL) | 12-18 | 15 | |
| | | OL 22 | Day 22 (OL) | 19-25 | 22 | |
| | | OL 28 | Day 28 (OL) | 26 to end of OL | 28 | |
| | | OL final visit | End Point (OL) | 2 to end of OL | | |
| | OL FU | OL F/U 7 | Week 1 (OL F/U) | OL FU start day-10 | 7 | |
| | | OL F/U 14 | Week 2 (OL F/U) | 11-21 | 14 | |
| | | OL F/U 28 | Week 4 (OL F/U) | 22 to end of OL F/U | 28 | |
| | | OL F/U final visit | End Point (OL F/U) | 1 to end of OL F/U | | |
| POMS-2 | DB | 25 | Day 25 (DB) | 2 to end of DB | 25 | |
| | DB FU | DB F/U 7 | Week 1 (DB F/U) | DB F/U start day-10 | 7 | |
| | | DB F/U 14 | Week 2 (DB F/U) | 11-21 | 14 | |
| | | DB F/U 28 | Week 4 (DB F/U) | 22 to end of DB F/U | 28 | |
| | | DB F/U final visit | End Point (DB F/U) | 1 to end of DB F/U | | |
| | PT | 32 | Week 1 (PT) | PT start day to 35 | 32 | |
| | | 39 | Week 2 (PT) | 36-46 | 39 | |
| | | 53 | Week 4 (PT) | 47-60 | 53 | |
| | | 67 | Week 6 (PT) | 61-74 | 67 | |
| | | 81 | Week 8 (PT) | 75-95 | 81 | |
| | | 109 | Week 12 (PT) | 96-123 | 109 | |
| | | 137 | Week 16 (PT) | 124-151 | 137 | |
| | | 165 | Week 20 (PT) | 152-179 | 165 | |
| | OL FU | OL F/U 7 | Week 1 (OL F/U) | OL FU start day-10 | 7 | |
| | | OL F/U 14 | Week 2 (OL F/U) | 11-21 | 14 | |
| | | OL F/U 28 | Week 4 (OL F/U) | 22 to end of OL F/U | 28 | |
| | | OL F/U final visit | End Point (OL F/U) | 1 to end of OL F/U | | |
| | SDS | DB | 1 | Baseline (DB) | ≤1 (predose) | 1 |
| | | | 28 | Day 28 (DB) | 2 to end of DB | 28 |
| PT | | 39 | Week 2 (PT) | PT start day to 46 | 39 | |
| | | 53 | Week 4 (PT) | 47-60 | 53 | |
| | | 67 | Week 6 (PT) | 61-74 | 67 | |
| | | 81 | Week 8 (PT) | 75-95 | 81 | |
| | | 109 | Week 12 (PT) | 96-123 | 109 | |
| | | 137 | Week 16 (PT) | 124-151 | 137 | |
| | | 165 | Week 20 (PT) | 152-179 | 165 | |
| | | 193 | Week 24 (PT) | 180 to end of PT | 193 | |
| CGI-S | Screening /lead-in | | Week -6 (SL) | | | |
| | | | Week -4 (SL) | | | |
| | | | Week -2 (SL) | | | |
| | DB | 1 | Baseline (DB) | ≤1 (predose) | 1 | |
| | | 8 | Day 8 (DB) | 2-11 | 8 | |
| | | 15 | Day 15 (DB) | 12-18 | 15 | |
| | | 22 | Day 22 (DB) | 19-25 | 22 | |

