| | | 15 | Day 15: Predose (DB) Day 15: 40M (DB) Day 15: 1H (DB) Day 15: 1.5H (DB) | 14-16 | 15 | |
| | | 18 | Day 18: Predose (DB) Day 18: 40M (DB) Day 18: 1H (DB) Day 18: 1.5H (DB) | 17-20 | 18 | |
| | | 22 | Day 22: Predose (DB) Day 22: 40M (DB) Day 22: 1H (DB) Day 22: 1.5H (DB) | 21-23 | 22 | |
| | | 25 | Day 25: Predose (DB) Day 25: 40M (DB) Day 25: 1H (DB) Day 25: 1.5H (DB) | 24 to end of DB | 25 | |
| | | DB final visit | End Point (DB) | Day 1: 40M to end of DB | | |
| | | OL | OL 1 | Baseline (OL) Day 1: 40M (OL) Day 1: 1H (OL) Day 1: 1.5H (OL) | ≤ 1 / predose | 1 |
| | | | OL 4 | Day 4: Predose (OL) Day 4: 40M (OL) Day 4: 1H (OL) Day 4: 1.5H (OL) | 2-6 | 4 |
| | | | OL 8 | Day 8: Predose (OL) Day 8: 40M (OL) Day 8: 1H (OL) Day 8: 1.5H (OL) | 7-9 | 8 |
| | | | OL 11 | Day 11: Predose (OL) Day 11: 40M (OL) Day 11: 1H (OL) Day 11: 1.5H (OL) | 10-13 | 11 |
| | OL 15 | | Day 15: Predose (OL) Day 15: 40M (OL) Day 15: 1H (OL) Day 15: 1.5H (OL) | 14-16 | 15 | |

Table 1: Analysis Visits

| Parameter | Analysis Phase | Scheduled Day ^a | Time Interval (label on output) | Time Interval ^a (Day) | Target Time Point ^a (Day) |
|-----------------------------|--------------------|----------------------------|--|----------------------------------|--------------------------------------|
| | | OL 18 | Day 18: Predose (OL) Day 18: 40M (OL) Day 18: 1H (OL) Day 18: 1.5H (OL) | 17-20 | 18 |
| | | OL 22 | Day 22: Predose (OL) Day 22: 40M (OL) Day 22: 1H (OL) Day 22: 1.5H (OL) | 21-23 | 22 |
| | | OL 25 | Day 25: Predose (OL) Day 25: 40M (OL) Day 25: 1H (OL) Day 25: 1.5H (OL) | 24 to end of DB | 25 |
| | | OL final visit | End Point (OL) | Day 1: 40M to end of OL | |
| Weight and BMI | DB | Screening, 1 | Baseline (DB) | ≤ 1 / predose | 1 |
| | | 15 | Day 15 (DB) | 2-21 | 15 |
| | | 28 | Day 28 (DB) | 22 to end of DB | 28 |
| | | DB final visit | End Point (DB) | 2 to end of DB | |
| | OL | OL 1 | Baseline (OL) | ≤ 1 / predose | 1 |
| | | OL 15 | Day 15 (OL) | 2-21 | 15 |
| | | OL 28 | Day 28 (OL) | 22 to end of OL | 28 |
| | | OL final visit | End Point (OL) | 2 to end of OL | |
| ECG | DB | Screening, 1 | Baseline (DB) | ≤ 1 / predose | 1 |
| | | 1 | Day 1: 1H (DB) | 1 | 1 |
| | | 8 | Day 8: 1H (DB) | 2-11 | 8 |
| | | 15 | Day 15: 1H (DB) | 12-20 | 15 |
| | | 25 | Day 25: 1H (DB) | 21 to end of DB | 25 |
| | DB final visit | End Point (DB) | 2 to end of DB | | |
| | OL | OL 1 | Day 1: 1H (OL) | 1 | 1 |
| | | OL 15 | Day 15: 1H (OL) | 2-20 | 15 |

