6.2. Pharmacokinetic/Pharmacodynamic Relationships

The PK/PD analysis will be based on the PK/PD analysis set (defined in Section 2.4.6) for nominal time-matched plasma concentrations and safety parameters.

Safety parameter: blood pressure (DBP and SBP), QTcF and CADSS total score

- DBP and SBP: 40 minutes and 1 hour postdose, Day 4(DB), 25(DB) and Day 25(OL)
- QTcF: 1 hour postdose, Day 25(DB) and Day 25(OL)
- CADSS total score: 40 minutes, Day 4(DB), 25(DB) and Day 25(OL)

The following plots will be generated to evaluate the relationship between safety parameter (absolute value and change [change from predose for SBP, DBP and CADSS total score, change from baseline for QTcF]) and plasma concentrations of esketamine by phases:

- DBP at each time-matched point of measurement from each dose will be plotted against the corresponding plasma concentration of esketamine.
- SBP at each time-matched point of measurement from each dose will be plotted against the corresponding plasma concentration of esketamine.
- QTcF at each time-matched point of measurement from each dose will be plotted against the corresponding plasma concentration of esketamine.

- CADSS total score at each time-matched point of measurement from each dose will be plotted against the corresponding plasma concentration of esketamine.
- Additional plots will be produced, if deemed necessary.

Pearson product moment correlations (R^2) will be calculated for nominal time-matched plasma concentrations and safety parameter.

The above analyses will be repeated for noresketamine.

Population PK/PD (MADRS total score and possibly selected AEs as additional PD parameters) analysis may be evaluated. If there is any visual trend in graphical analysis, suitable models will be applied to describe the PK/PD relationships. Details will be given in a PK/PD analysis plan will be presented in a separate report.

REFERENCES

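### SAP Table 1 has no Week 24 posttreatment window for POMS-2, so a scheduled assessment falls outside the by-visit summary

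*SAP*

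**What the plan says.** **POMS-2.** Time and Events Schedule 2 marks POMS-2 in the column headed "4.12 4.16 4.20 4.24", study days "109 137 165 193", and at early withdrawal. Protocol 11.8 states that "abuse-liability data from POMS-2 will be summarized descriptively at each scheduled visit by treatment group". SAP 5.5.7 likewise plans POMS-2 scores and changes from baseline at each time point of the posttreatment and follow-up phases.

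SAP 2.3 introduces Table 1 as giving the windows for every protocol visit in all phases. The POMS-2 posttreatment rows are for Days 32, 39, 53, 67, 81, 109, 137 and 165. The last is "165 | Week 20 (PT) | 152-179 | 165", and the next POMS-2 row belongs to the open-label follow-up phase. The Week 20 wording also occurs under SDS, CGI-S and C-SSRS, but there it is followed by a Week 24 row; for SDS this reads "193 | Week 24 (PT) | 180 to end of PT | 193".

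**Open-label vital signs.** The Day 25 row in the same table ends with "Day 25: 1.5H (OL) | 24 to end of DB | 25". Footnote a to Table 1 counts open-label days from the first day of that phase.

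**The concern.** A visit window is an operative rule: a programmer who follows Table 1 can tabulate only what falls inside a listed interval. For POMS-2 the last posttreatment interval is closed at Day 179, so the Week 24 scores are collected and then assigned to no visit. Subjects who stay relapse-free for 24 weeks finish the study without a follow-up phase (protocol 3.1 and 6.4), so no later POMS-2 stands in for the missing one. What is at stake is the final off-drug mood assessment of the longest-followed responders, which both documents say will be summarised.

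The open-label vital-sign row raises a smaller version of the same problem, because its upper limit names the wrong phase.

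**Working it through.** **1. Reproducing the SAP's own limits.** The inputs are the POMS-2 posttreatment target days in SAP Table 1, plus Day 193 from Schedule 2. The rule that fits is: upper limit = (target + next target) / 2, rounded down.

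| Target | Next target | Midpoint, rounded down | SAP upper limit |
|---|---|---|---|
| 32 | 39 | 35 | 35 |
| 39 | 53 | 46 | 46 |
| 53 | 67 | 60 | 60 |
| 67 | 81 | 74 | 74 |
| 81 | 109 | 95 | 95 |
| 109 | 137 | 123 | 123 |
| 137 | 165 | 151 | 151 |
| 165 | 193 | 179 | 179 |

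All eight limits reproduce. The last, (165 + 193) / 2 = 179, arises only if a Day 193 visit follows. Had Week 20 been meant as the final POMS-2 visit, its interval would be expected to run to the end of the phase, as the final rows of the other scales do.

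**2. Which permitted Week 24 days are covered.** Schedule 2 allows Day 193 ± 3, that is Days 190 to 196. The last window closes at Day 179, which is 190 − 179 = 11 days before the earliest permitted visit. None of the 7 permitted days lies in a POMS-2 posttreatment window. With a row from Day 180 to the end of the phase, all 7 do.

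**3. Who is affected.** Table 1 counts posttreatment days from the first day of the double-blind phase. The gap takes in all Week 24 completers and any early-withdrawal POMS-2 from Day 180. Subjects who relapse more than 20 weeks into the phase are withdrawn. Taking the phase to start on about Day 29 (SAP 2.1.2, with a Day 28 double-blind end), 20 weeks is about 29 + 140 = Day 169. Late withdrawals on about Days 169 to 179 therefore still fall in the Week 20 window.

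**4. Rough headcount.** The documents give no response or relapse rates for this trial. Assuming 20% to 40% responders among 183 subjects, and 30% to 60% of those relapse-free and still in the study at Week 24:
- low: 183 × 0.2 × 0.3 ≈ 11;
- high: 183 × 0.4 × 0.6 ≈ 44.

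**5. Open-label vital signs.** The limits of the preceding rows (6, 9, 13, 16, 20, 23) follow the same midpoint rule, and the last, (22 + 25) / 2 rounded down = 23, gives the stated lower limit of 24 for Day 25. For the upper limit, assume the scheduled days: last double-blind dose on Day 25, double-blind end on Day 28, and open-label start no earlier than 25 + 14 = Day 39. By the SAP 2.1.3 formula for events before a phase starts, the double-blind end is then open-label Day 28 − 39 = −11, or earlier still if the phase starts later. An interval from 24 to −11 is empty, and Days 24 to 26 (25 ± 1) are not in the preceding window, 21 to 23.

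**The case against.** The best defence on POMS-2 is that little of clinical interest is lost. The protocol says: "In the first 4 weeks of the posttreatment phase, withdrawal or rebound symptoms or both and potential abuse-liability will be evaluated". POMS-2 at Weeks 1, 2 and 4 has windows, as do Weeks 6 to 20. That limits the impact and stands. It does not explain the gap, since the SAP itself windows POMS-2 well beyond 4 weeks and commits to every posttreatment time point. A further caution is that the table was read as text extracted from a PDF, so a row lost in conversion cannot be wholly excluded; the neighbouring rows are intact.

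The defence on open-label Day 25 vital signs is stronger and largely succeeds. The row, its labels, lower limit and target are all present. The Day 25 rows for MOAA/S, oxygen saturation, BPRS+, CADSS, CGADR and pharmacokinetics end at the end of the open-label phase, so the intended reading is plain. Even read literally, the vital-sign End Point (OL) interval takes in Day 25, and the abnormality and acute-hypertension summaries in SAP 5.3 run over the whole phase.

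A reader might also infer that all open-label blood-pressure and concentration pairs are lost, because Day 25 is the only open-label day with pharmacokinetic sampling. The SAP does not support that. Section 6.2 names the times directly ("DBP and SBP: 40 minutes and 1 hour postdose, Day 4(DB), 25(DB) and Day 25(OL") and, with 2.4.6, pairs values by nominal time without citing the vital-sign window. The exclusion of samples outside the windows in 6.1.1 applies to descriptive statistics of plasma concentrations, and the Day 25 (OL) pharmacokinetic window is correctly stated.

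**Conclusion.** The POMS-2 omission holds. As written, Table 1 leaves posttreatment POMS-2 scores from Day 180 onward without an analysis visit, contrary to protocol 11.8 and SAP 5.5.7. The number affected is perhaps 11 to 44 subjects, on assumed rates that have no source in the documents. That is a headcount only and implies no effect on any conclusion.

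The vital-sign limit is an evident slip. Read literally, it would touch only the by-visit Day 25 (OL) rows.

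Three stronger readings are tempting, and the documents do not bear them out:
- that both sets of data fall out of all planned summaries (the open-label vital signs do not);
- that every withdrawal for relapse after Week 20 is lost (only those assessed from Day 180 are);
- that the pharmacokinetic/pharmacodynamic plots lose their open-label data.

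The consequence is limited to descriptive by-visit safety summaries, with no bearing on the primary endpoint.

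**What to change.** In SAP Table 1, under POMS-2 in the posttreatment phase, add a row identical to the one SDS already has: scheduled day 193, label Week 24 (PT), interval from Day 180 to the end of that phase, target Day 193. In the same edit, change the upper limit of the open-label Day 25 vital-sign interval to the end of the open-label phase.

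The cost is one row and one cell, with no new data and no change to any analysis method. The SAP amendment history shows the sponsor already making corrections of this kind in Section 2.3: Amendment 3 added two posttreatment rows for PWC-20, and Amendment 2 corrected a double-blind label that belonged to the open-label phase.

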2.4. Analysis Sets

Subjects will be classified into the following analysis sets: all randomized, full, safety, pharmacokinetic and PK/PD.

2.4.1. All Randomized Analysis Set

This analysis set will include all subjects who were randomized (ie, subjects who reported a randomization date, or were assigned a randomization number) regardless of whether or not treatment was received. This analysis set will be used for summarizing the overall study completion/withdrawal information.

2.4.2. Full Analysis Set (FAS)

Efficacy analysis will be performed on the following FAS.

FAS (DB): All randomized subjects who received at least 1 dose of intranasal study medication during the DB induction phase.

FAS (OL): All subjects who received at least 1 dose of intranasal study medication during the OL induction phase.

FAS (responders): All randomized subjects who receive at least 1 dose of intranasal study medication during the double-blind induction phase and who are responders at the end of the double-blind induction phase and entered the posttreatment phase.

2.4.3. Safety Analysis Set

The following safety analysis sets are defined for each phase. Analyses of change from baseline will include only those subjects who have baseline and at least 1 postbaseline observation in that phase.

Safety (DB): All randomized subjects who receive at least 1 dose of intranasal study medication in the DB induction phase.

Safety (OL): All subjects who receive at least 1 dose of intranasal study medication in the OL induction phase.

Safety (responders): All randomized subjects who receive at least 1 dose of intranasal study medication during the double-blind induction phase and who are responders at the end of the double-blind induction phase and entered the posttreatment phase.

Screen failures and randomized subjects who received no study medication will be excluded from the safety analysis set. Subjects who received an incorrect treatment will be analyzed under the planned treatment.

2.4.4. Follow-up Analysis Set

The following FU analysis sets are defined for each phase and will be used for both safety and efficacy analyses.

- FU (DB): All subjects who do not respond at the end of DB induction phase and enter the DB follow-up phase
- FU (OL): All Safety (OL) subjects who enter the OL follow-up phase

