Responders who completed the double-blind induction phase will enter the 24-week posttreatment phase to evaluate durability of efficacy after cessation of add-on intranasal esketamine or placebo treatment while continuing the oral antidepressant treatment regimen, as assessed by the time to relapse and proportion of responders and remitters at each visit in this phase. All subjects who are discontinued must be treated with an oral antidepressant after completion of the study, unless it is clinically inappropriate.

Open-label Induction Phase

Subjects who relapsed in the posttreatment phase will receive a 4-week open-label induction treatment course of intranasal esketamine. The beginning of the OL induction phase should be at least 2 weeks (14 calendar days) after the last dose in the double-blind induction phase. Subjects who meet the relapse criteria before 2 weeks after the last dose in the double-blind induction

phase will not have an option for joining open label induction phase. They will withdraw from the posttreatment phase and move forward to the follow up phase.

[figure not shown]
Subjects who enter the OL induction phase will start treatment sessions with 56 mg of intranasal esketamine on the first day of OL induction phase (Day 1 OL). On the fourth day (Day 4 OL), the dose will be increased to 84 mg. On Day 8 OL and Day 11 OL, the dose may remain the same as 84 mg or could be reduced by 28 mg as determined by the investigator based on efficacy and tolerability. On Day 15 OL, a dose reduction is permitted if required for tolerability; no dose increase is permitted on Day 15 OL. After Day 15 OL, the dose should be stable (unchanged). If needed for tolerability, a dose reduction is permitted from Day 15 OL until Day 25 OL.

The oral antidepressant medication initiated from the prospective lead-in phase, which will continue in the posttreatment phase will also be maintained throughout this phase.

Follow-up Phase

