2. GENERAL ANALYSIS DEFINITIONS

2.1. Analysis Phases

There are 5 analysis phases defined in this study:

- *A Double-blind Induction Phase*
- *A Double-blind Follow-up Phase* (Non-Responders or subjects who withdraw from DB induction phase)
- *A Posttreatment Phase* (Responders only)
- *An Open-Label Induction Phase* (Responders only)
- *An Open-Label Follow-up Phase* (Responders only)

Each analysis phase has its own analysis phase start and end dates.

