2.1.2. Analysis Phase Start and End Dates

Double-blind Induction Phase

The start date of the double-blind induction phase (referred to as ‘DB start date’) is the date of the first dose of intranasal study medication. The double-blind induction phase end date (referred to as ‘DB end date’) is the maximum of the date of the last visit in the double-blind induction phase and the date of completion/withdrawal from the double-blind induction phase.

The start date/time of the double-blind induction phase (referred to as, ‘DB start date/time’) is the DB start date and the time of the first dose of intranasal study medication.

Double-blind Follow-up Phase

The start date of the double-blind follow-up phase (referred to as ‘DB FU start date’) is the day after the DB end date. The double-blind follow-up phase end date (referred to as ‘DB FU end date’) is the maximum of the last DB follow-up visit date or the end of trial date.

Posttreatment Phase

The start date of the posttreatment phase (referred to as ‘PT start date’) is the day after the DB end date. The posttreatment phase end date (referred to as ‘PT end date’) is defined as: for subjects who entered OL phase, the day of OL start date (defined below); for subjects who did not enter OL, including responders who withdraw within 4 weeks after the last dose of DB intranasal drug, the maximum of the last posttreatment visit date or the end of trial date.

For subjects who entered OL phase, PT end date/time is one minute before OL start date/time (defined below).

Open-Label Induction Phase

The start date of the open-label induction phase (referred to as ‘OL start date’) is the date of the first dose of intranasal study medication in a second induction treatment course. The open-label induction phase end date (referred to as ‘OL end date’) is the maximum of the date of the last visit in the open-label induction phase and the date of completion/withdrawal from the open-label induction phase.

The start date/time of the open-label induction phase (referred to as, ‘OL start date/time’) is the OL start date and the time of the first dose of intranasal study medication in the second induction treatment course.

Open-Label Follow-up Phase

The start date of the open-label follow-up phase (referred to as ‘OL FU start date’) is the day after the OL end date. The open-label follow-up phase end date (referred to as ‘OL FU end date’) is the maximum of the last OL follow-up visit date or the end of trial date.

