4. EFFICACY

Efficacy summaries for the DB induction phase and the OL induction phase will be based on FAS (DB) and FAS (OL), respectively. FAS (responders) will be applied for the summaries in posttreatment phase and for the analysis for time to relapse. Summaries for DB/OL follow up phase will be based on FU(DB)/ FU (OL).

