5. SAFETY

All safety summaries for induction phases will be based on the safety analysis sets described in Section 2.4.3. Safety summaries for the follow-up phases will be based on the follow-up analysis sets described in Section 2.4.4.

Unless specified otherwise, Baseline (DB) will be used for DB induction phase and DB follow-up phase. Baseline (OL) will be used for OL induction phase and OL follow-up phase.

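### FU (DB) is limited to nonresponders, so read literally it omits subjects who withdraw from double-blind induction while responding, although SAP 2.1 places them in the double-blind follow-up phase

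*SAP*

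**What the plan says.** - **Who is in the phase.** SAP 2.1 describes the DB follow-up phase as covering "Non-Responders or subjects who withdraw from DB induction phase". The second group carries no response condition. Protocol 3.1 and 9.1.5 agree: a subject who leaves DB induction for any reason other than withdrawal of consent has an early-withdrawal (EW) visit and then 4 weeks of follow-up.
- **Who is in the set.** SAP 2.4.4 defines FU (DB) as "All subjects who do not respond at the end of DB induction phase and enter the DB follow-up phase". The open-label counterpart, in the next line, is "All Safety (OL) subjects who enter the OL follow-up phase", with no response condition.
- **What the set is used for.** SAP 5 states: "Safety summaries for the follow-up phases will be based on the follow-up analysis sets described in Section 2.4.4". SAP 4 does the same for efficacy summaries in the follow-up phases.
- **The nearest alternative set.** Safety (responders) in SAP 2.4.3 takes subjects "who are responders at the end of the double-blind induction phase and entered the posttreatment phase". SAP 1.2 restricts that entry: "Responders who completed the double-blind induction phase will enter the 24-week posttreatment phase".

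**The concern.** The phase has two entry routes and the set that summarises it names only one. A subject who withdraws while meeting the response threshold is in the phase but, on the wording, not in the set. Membership then turns on response, a post-randomisation outcome, so any omission could differ between arms.

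Withdrawal or rebound symptoms after stopping esketamine are a named safety objective (SAP 1.1). Protocol 6.5 asks for the oral antidepressant to be continued in follow-up, unless clinically inappropriate, so that such symptoms can be judged. Protocol 11.8 says all reported AEs will be analysed. A summary of the phase that omits some of the people in it falls short of these aims, even if the number is small.

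**Working it through.** This is mainly a check of set definitions. Take a subject who stops DB treatment early, does not withdraw consent, has at least 50% MADRS improvement at the last DB assessment, and enters follow-up.

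| Phase or set | Condition in the SAP | Is the subject in it? |
|---|---|---|
| DB follow-up phase (2.1) | Nonresponder, or withdrew from DB induction | Yes, by withdrawal |
| FAS (DB), Safety (DB) (2.4.2, 2.4.3) | Randomised and dosed | Yes, but SAP 4 and 5 assign these to the induction phase |
| FU (DB) (2.4.4) | Nonresponse at end of DB induction, and entered follow-up | No, on the literal wording |
| FAS/Safety (responders) (2.4.2, 2.4.3) | Responder, and entered posttreatment | No, did not complete DB |
| FU (OL) (2.4.4) | Safety (OL), and entered OL follow-up | No, no OL dose |

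**Can a withdrawer be a responder at the end of DB?** The SAP allows it. Section 2.1.2 sets the DB end date for each subject, as the later of the last DB visit and "the date of completion/withdrawal from the double-blind induction phase". Section 2.2 takes End Point (DB) as the last postbaseline value in the phase. Section 4.3.1.1 defines response at a given time point. The EW visit includes a MADRS (Protocol, Time and Events Schedule 1).

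**Summaries that depend on FU (DB):** AEs in DB follow-up (5.1), C-SSRS (5.5.1), PWC-20 (5.5.6), POMS-2 (5.5.7), and descriptive CGI-S and MADRS in that phase (4.3.5.2, 4.3.8.2).

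**Number affected.** Protocol 11.2 and SAP 1.4 give 72 + 3 × 37 = 183 randomised and 12.5% dropout.

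- Planned dropouts: 183 × 0.125 = 22.9, about 23.
- The share responding at withdrawal is not in the documents. With assumed shares:
  - 10%: 22.9 × 0.10 = 2.3, about 2
  - 25%: 22.9 × 0.25 = 5.7, about 6
  - 50%: 22.9 × 0.50 = 11.4, about 11

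For any assumed share these are upper bounds, since subjects who withdraw consent have no follow-up and those lost to follow-up contribute little or nothing.

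**The case against.** **Withdrawers may be nonresponders by construction.** Protocol 3.1 ends the DB phase at Day 28, and Protocol 4.3.2 judges response at the end of the 4-week phase. Someone who stops on Day 18 has an EW visit within a week, by Day 25. That falls outside the Day 28 MADRS window (Day 26 to end of DB, SAP Table 1), so Day 28 is missing. SAP 4.1.2 then scores missing as nonresponse. Sections 4.3.1.2, 4.3.2.2 and 4.3.4.1 likewise count early discontinuation as failure. The Amendment 1 log says the 2.4.4 sets were updated to follow the analysis phases, which suggests that withdrawers were meant to be included.

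This reading is possible, and it is why the point cannot be put as a certain exclusion. It does not settle the matter. Each of those rules is stated for a particular response or remission analysis and none is tied to set membership. SAP 2.1 lists withdrawers separately from nonresponders, which would be redundant if every withdrawer were a nonresponder. On this reading the definition is still ambiguous, and two programmers could build different sets.

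**Much of these subjects' data is reported elsewhere.** This stands.

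- AEs up to the DB end date, which can run to the EW visit, are in the DB-phase TEAE tables on Safety (DB).
- PWC-20 at the end of induction is tabulated.
- Disposition for DB follow-up (SAP 3.2) is not restricted to FU (DB).
- Follow-up MADRS scores from withdrawers enter the MMRM sensitivity analysis on FAS (DB) (SAP 4.2.3.4).
- Deaths, other SAEs and discontinuations due to AEs are listed without restriction to a set (SAP 5.1).

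A reader might infer that these subjects' post-cessation events disappear from the report. They do not: the gap is confined to the by-phase summaries of DB follow-up. For non-serious follow-up AEs and follow-up PWC-20 scores, however, SAP 5.1 and 5.5.6 name no listing that would fill it.

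**Conclusion.** The inconsistency between SAP 2.1 and 2.4.4 is real and should be corrected. On the literal text, a subject who withdraws from DB induction while responding is in no set used to summarise DB follow-up. On the favourable reading, the definition is ambiguous. About 2 to 11 subjects could be affected, assuming 12.5% dropout and 10% to 50% responding at withdrawal; only the first of these two figures comes from the documents.

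A reader might also infer that the omitted subjects are mainly people who improved but could not tolerate esketamine, or that the set was chosen to leave them out. The documents support neither. Protocol 10.2 lists lack of efficacy, noncompliance with the oral antidepressant, protocol violation, a broken blind and pregnancy among the withdrawal reasons, and nothing gives response status or arm by reason. The wording looks like shorthand that did not keep pace with the phase definition.

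Responders who leave the posttreatment phase within 4 weeks of the last DB dose are not part of this gap: SAP 2.1.2 keeps them in the posttreatment phase. The primary analysis and the sample size are untouched.

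**What to change.** In SAP 2.4.4, define FU (DB) as all Safety (DB) subjects who enter the DB follow-up phase (nonresponders, or subjects who withdraw from DB induction), regardless of response. This matches SAP 2.1 and the form already used for FU (OL).

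The cost is one sentence and no new data. If the tables were programmed on the narrower set, the DB follow-up summaries need to be re-run. If every withdrawer is already included, no output changes and the sentence only records what was done.
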